8.2 Medical/Surgical History

General medical and surgical history, and ocular medical and surgical history reported in eCRF will be coded using the Medical Dictionary for Regulatory Activities (MedDRA version 23.1 - September 2020). General medical and surgical history will be summarized by system organ class (SOC) and preferred term for past and current medical conditions separately. Subjects reporting more than one medical condition in a SOC will be counted only once in that SOC. Ocular medical and surgical history will be summarized by SOC and preferred term for the study eye and non-study eye separately.

Data listings of general medical and surgical history, and ocular medical and surgical history will be provided.

8.3 Prior and Concomitant Medications

Prior and concomitant medications, including rescue medications, will be coded using the World Health Organization (WHO) Drug Dictionary (B3 WHO Drug Global - September 2020). When medications cannot be coded, the name entered in the eCRF will be reported.

A summary of concomitant medications taken during the course of the study will be tabulated by Anatomical Therapeutic Chemical (ATC) Classification and WHO drug name. The summary will exclude prior medications with a stop date prior to the date of first dose of the study drug or follow-up medications with a start date after the last day of the Main study (EOMS). Medications used as part of the routine surgical procedure and rescue medications will be summarized separately.

All prior and concomitant medications will be presented in a data listing.

9. TREATMENT COMPLIANCE

Overall treatment compliance per subject for the study eye is defined as:

Treatment compliance (%) = [Total number of doses instilled correctly / (Actual treatment duration) x 2] x100,

where the actual treatment duration is calculated as the number of days between the first dose date and last dose date of study drug.

The treatment compliance will be summarized using descriptive statistics for the Safety population. In addition, the overall treatment compliance will be further categorized as < 80%, 80% – 100% and > 100%, and the number and percentage of subjects with compliance in each category will be presented.

Subject dosing diary data will be listed.

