10.2 ANALYSIS POPULATIONS

The analysis populations are defined as follows:

- Intent-to-Treat (ITT) Population: All subjects who are randomized to study drug. Following the ITT principle, subjects will be analyzed according to the treatment they are assigned to at randomization.

- Per-protocol (PP) Population: All subjects in the ITT population who (i) received at least 1 dose of study drug, (ii) do not have major protocol deviations that would impact the evaluation of efficacy and (iii) have at least 80% overall dosing compliance.
- Safety Population: All randomized subjects who receive at least one dose of study drug.

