5.2 Per-protocol (PP) Population

The PP population will consist of all subjects in the ITT population who (i) receive at least 1 dose of study drug, (ii) do not have major protocol deviations that would impact the evaluation of efficacy, and (iii) have at least 80% overall treatment compliance.

The subjects who are to be excluded from the PP population will be identified prior to database lock and unmasking of the treatment assignment and the reason for exclusion will be documented and listed.

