6.3.4 Study Day, End of Main Study (EOMS) and End of Sub-Study (EOSS)

Study Day for each subject is calculated relative to the date of the first dose of study drug:

- Study Day = Visit Date/Event Date - Date of First Dose +1
When the Visit Date/Event Date is on or after the Date of First Dose
- Study Day = Visit Date/Event Date - Date of First Dose
When the Visit Date/Event Date is prior to the Date of First Dose

Study Day will be used to define analysis windows for efficacy analyses and to evaluate the timing of events or measurements occurring relative to the first dose of study drug.

Study Day ‘-1’ corresponds to Surgery Day 0 and Study Days ‘-29’ to ‘-2’ correspond to Screening Visit (Days -28 to -1) as shown in the Schedule of Events (Table 2).

EOMS will be either Visit 6/POD22 for all randomized subjects who complete the Main study or the Early Termination/Withdrawal visit for subjects who discontinue the Main study prior to Visit 6/POD22.

EOSS for the subjects in the Endothelial Cell Sub-study will be either Visit 7/POD85 for subjects who complete the Sub-study or the Early Termination/Withdrawal visit for subjects who discontinue the Sub-study prior to Visit 7/POD85.

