11.1 Extent of Exposure

Exposure to study drug will be summarized by duration (days) on study drug (the number of days between the first dose date and last dose date of study drug) and total number of doses that are instilled correctly in the study eye using descriptive statistics for all subjects in the Safety population and subjects in the Sub-Study. In addition, the duration on study drug will be categorized as 1–4 days, 5–8 days, and 9–13 days, and ≥ 14 days, and the number and percentage of subjects in each category will be presented for all subjects in the Safety population and subjects in the Sub-Study. The number of doses received per subject will also be categorized as < 8 doses, 8–< 16 doses, 16–< 28 doses, = 28 doses, and >28 doses, and the number and percentage of subjects in each category will be presented by treatment group for all subjects in the Safety population and subjects in the Sub-Study.

If the date of last dose is missing, the date of the last scheduled or unscheduled visit will be used as the date of last dose to calculate the treatment duration.

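### SAP 9 prints the compliance formula with the factor 2 as a multiplier, so a full course scores 400% or more and 6 of 28 doses meet the 80% per-protocol criterion

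*SAP*

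**What the plan says.** The PP population has three conditions, one of which is a compliance threshold. Protocol 10.2 requires that subjects "have at least 80% overall dosing compliance", and SAP 5.2 that they "have at least 80% overall treatment compliance". The protocol gives no formula. The only one is in SAP 9, inside an outer pair of square brackets: "Total number of doses instilled correctly / (Actual treatment duration) x 2] x100".

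SAP 9 adds that "the actual treatment duration is calculated as the number of days between the first dose date and last dose date of study drug". It then states that "the overall treatment compliance will be further categorized as < 80%, 80% – 100% and > 100" per cent.

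SAP 11.1 uses the same wording for exposure, "duration (days) on study drug (the number of days between the first dose date and last dose date of study drug", and states that "the duration on study drug will be categorized as 1–4 days, 5–8 days, and 9–13 days, and ≥ 14 days". By contrast, SAP 6.3.4 writes the extra day out for dates on or after first dose: "Study Day = Visit Date/Event Date - Date of First Dose +1".

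The PP analysis of both primary endpoints is a sensitivity analysis in SAP 10 and 10.1.3, and is described as supportive in Protocol 10.8.

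**The concern.** Dosing is twice daily from POD1 to POD14. A sensible compliance measure divides the doses taken by two per day on treatment, so that a perfect course gives 100%. The three SAP 9 bands make sense only on that scale. The printed expression divides by days and then multiplies by 2, which is four times the intended value for the same day count. An 80% threshold applied to it works like a 20% threshold.

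At stake is whether the PP population means what it says. Followed literally, subjects with well under half of the planned doses stay in the PP analysis, and full compliers appear in the band above 100%. The day count is a second, lesser matter. The wording does not settle it, and one of its two readings puts full-course subjects in the wrong exposure band.

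**Working it through.** **Inputs.** Two doses a day for 14 days, POD1 to POD14 (Protocol Table 1; SAP 3.1 and Table 2); PP threshold 80% (SAP 5.2); formula and duration wording (SAP 9); duration and dose-count bands (SAP 11.1).

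**The plan's own figure.** 2 × 14 = 28 doses, which matches the separate category for exactly 28 doses in SAP 11.1. The documents give no worked compliance percentage.

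**Formulas.** N is the number of correctly instilled doses and D the duration in days.
- As printed: N / D × 2 × 100
- Brackets repaired: N / (2 × D) × 100
- From first dose on POD1 to last dose on POD14, D = 14 if both end dates count, or 14 − 1 = 13 as a date difference.

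**Results in per cent, first dose POD1 and last dose POD14.**

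| Doses N | Printed, D = 14 | Printed, D = 13 | Brackets repaired, D = 13 | Both repaired, D = 14 |
|---|---|---|---|---|
| 28 | 400.0 | 430.8 | 107.7 | 100.0 |
| 23 | 328.6 | 353.8 | 88.5 | 82.1 |
| 22 | 314.3 | 338.5 | 84.6 | 78.6 |
| 21 | 300.0 | 323.1 | 80.8 | 75.0 |
| 20 | 285.7 | 307.7 | 76.9 | 71.4 |
| 14 | 200.0 | 215.4 | 53.8 | 50.0 |
| 6 | 85.7 | 92.3 | 23.1 | 21.4 |
| 5 | 71.4 | 76.9 | 19.2 | 17.9 |

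**Fewest doses that reach 80%.**
- Printed, D = 14: 0.8 × 14 / 2 = 5.6, so 6.
- Printed, D = 13: 0.8 × 13 / 2 = 5.2, so 6.
- Brackets repaired, D = 13: 0.8 × 26 = 20.8, so 21 (21/28 = 75% of plan).
- Both repaired, D = 14: 0.8 × 28 = 22.4, so 23.

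In general the printed rule passes anyone with N ≥ 0.4 × D. That is 0.4 doses per counted day against 2 planned.

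**Day count.** The SAP 11.1 bands start at 1 day and end at 14 or more, which fits an inclusive count: a one-day course is 1 and a full course is 14. Under a date difference a full course is 13 and falls in the 9–13 band. A one-day course has D = 0, which fits no band and makes compliance undefined.

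**Does the deviation rule catch under-dosing instead?** Protocol 8.5.2 reports under-dosing only once at least two days in a row pass with no dose at all.
- Six doses over POD1 to POD14 are always caught. Without a two-day gap, successive dosing days are at most 2 days apart, so six dosing days make five steps covering at most 10 of the 13 days needed. Even then, 8.5.2 gives no numeric line between major and minor.
- One dose a day (14 of 28) never leaves a day without a dose. It is not an 8.5.2 deviation, yet it scores at least 200% as printed.

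**The case against.** The strongest reply is that this is a bracket slip with an obvious intent. A programmer would code doses over twice the duration. If not, the first run would show every full-course subject at 400% or more. PP exclusions and deviations are also reviewed before lock and unmasking (SAP 5.2 and 7.2). It could further be argued that the formula was meant as a stacked fraction with the 2 below the line. The intent is indeed clear, and if the programs already follow it, no result changes. But the text closes the parentheses around the duration alone, nothing in the documents shows a stacked fraction, and no other section states the formula correctly. A rule that defines a prespecified population should not depend on the programmer correcting it.

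Other safeguards exist. Diaries are checked at visits and subjects re-instructed (Protocol 5.1.2.2), and the SAP 11.1 dose-count table does not use the formula. Heavy under-dosing therefore stays visible. None of this changes who passes the 80% criterion.

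Four stronger readings are tempting, and the documents do not support them:
- **That the missing +1 is a second definite error.** It is an ambiguity. The 11.1 bands point to an inclusive count, so the misplaced exposure band and the zero duration arise only if a plain date difference is coded.
- **That 8.5.2 sets a floor of 8 doses.** That holds only if the last dose is on POD14. Seven single doses on PODs 1, 3, 5, 7, 9, 11 and 13 also avoid a deviation. The printed cut-off over POD1 to POD14 is 6.
- **That using actual instead of planned duration is wrong.** A subject who takes 8 doses in 4 days and stops scores 8 / (2 × 4) = 100% under the repaired, inclusive formula. This measures adherence while on drug. Early stopping is reported separately in SAP 7.1 and 11.1.
- **That the primary result is at risk.** The primary analysis is on the ITT population and does not use compliance.

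**Conclusion.** The point holds. The SAP 9 formula is wrong as written under either day count, and as printed it makes the 80% condition nearly empty. The expectation that almost nobody would be excluded assumes that few subjects average below 0.4 doses a day; the documents give no compliance distribution.

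The day-count wording needs clarifying but is not itself shown to be wrong. It matters because repairing the brackets alone is not enough if a date difference is coded: a perfect course would then sit above 100%, and 21 or 22 doses would pass where the inclusive count fails them.

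The reach is limited to the compliance table, the PP sensitivity analysis of the two primary endpoints and, under the date-difference reading only, the exposure-duration table. It should be corrected, but it does not bear on the trial's main conclusion.

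**What to change.** In SAP 9 and SAP 11.1, print: duration (days) = last dose date − first dose date + 1.

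In SAP 9, print: compliance (%) = 100 × correctly instilled doses / (2 × duration).

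No other change is needed. The threshold, the bands and the PP definition can stay as they are.

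The cost is a wording change to the SAP and a check that the programs match it. The inputs are the diary data already entered in the eCRF. It should be done before database lock and unmasking, since SAP 5.2 requires PP exclusions to be settled by then.

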8.5.2 Under-dose

Under-dosing will not be reported as a protocol deviation until the subject has missed both of the doses on 2 or more consecutive days.

The importance of the protocol deviation (major/minor) will be determined by the amount of dosing under that specified in the protocol.

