3. STUDY DESIGN

3.1 Study Design Overview

This Phase 3 study will evaluate APP13007 [REDACTED] in comparison to the matching vehicle placebo in a randomized, parallel-group, double-masked fashion. Subjects will have routine uncomplicated cataract surgery on Day 0 of the study and will be assessed the next day (POD1) after the surgery for eligibility for randomization to study treatment. The study comprises the Main Study and the Endothelial Cell Sub-study. All randomized subjects (approximately 370) will participate in the Main Study. The Endothelial Cell Sub-study will comprise a subgroup of approximately 176 subjects at study sites qualified to perform corneal endothelial cell parameter assessments.

All eligible subjects at the qualified study sites for corneal endothelial cell assessments will be requested to participate in the Sub-study. If a subject is unable or unwilling to participate in the Sub-study, the Investigator has the option to enroll the subject in the Main Study only, after consulting with the Study Medical Monitor.

Subjects who experience postoperative inflammation on POD1 and who meet all other eligibility criteria will be randomized, at a 1:1 ratio, to one of two study treatments (either Treatment 1 or Treatment 2):

[figure not shown]
- Treatment 1: 1 drop APP13007 twice daily (BID) (morning and evening) for 14 days instilled to the operated study eye
- Treatment 2: 1 drop matching vehicle placebo BID (morning and evening) for 14 days instilled to the operated study eye

After randomization, the first dose of study drug will be administered in the clinic on POD1 so that the site personnel can ensure the subject is able to administer the study drug correctly. The second drop of the study drug on POD1 will be administered by the subject a minimum of 6 hours later. For all other days, the first dose will be instilled in the morning and the second dose instilled a minimum of 6 hours, but preferably 8 to 12 hours, later. The number of drop(s) instilled and the date/time of instillation of each dose will be recorded by the subject in the subject's dosing diary. The study drug will be dosed BID for 14 days.

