6.4.3 Handling Dropouts or Missing Data

6.4.3.1 Imputation of Missing Efficacy Data

The missing data handling rule for the study eye will be applied for the efficacy endpoints.

Missing data from subjects who discontinue the study before POD15 assessments without taking rescue medication:

For subjects who prematurely discontinue the study without taking rescue medication, the LOCF approach will be used to impute the missing data. The last observation will be the last assessment value after the first dose of study drug and up to two days following the last dose of study drug.

Missing data from subjects who discontinue the study before POD15 assessments and take rescue medication before POD15 assessments:

For both categorical and continuous secondary efficacy endpoints of ACC grade, ocular pain grade and ACF grade, subjects who take rescue medication before POD15 assessments and prematurely discontinue the study, the LOCF approach will be used to impute the missing data. The last observation will be the last assessment value after the first dose of study drug and prior to starting rescue medication.

Intermittent missing data:

The likelihood of having intermittent missing data is low. For subjects with intermittent missing data for efficacy endpoints, the LOCF approach will be applied to impute the missing data, i.e., using the data collected from the most recent prior visit after the first dose of study drug.

If no data can be carried forward (i.e., missing assessments at POD 4 visit or no available post-baseline assessments), missing data will be treated as missing for the continuous endpoints and will be considered as 'Non-responder' for the categorical endpoints.

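### SAP 9 measures compliance only up to each subject's own last dose, so the 80% Per-Protocol criterion cannot detect early stopping

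*SAP*

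**What the plan says.** The course is fixed in SAP 3.1: "The study drug will be dosed BID for 14 days". That is 28 doses, and the dose categories in SAP 11.1 use 28 as the full count.

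SAP 9 defines overall compliance as "Treatment compliance (%) = [Total number of doses instilled correctly / (Actual treatment duration) x 2] x100". The line below the formula then says how its denominator is obtained: "where the actual treatment duration is calculated as the number of days between the first dose date and last dose date of study drug".

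SAP 5.2 builds the PP set from ITT subjects who have had at least one dose and who (ii) "do not have major protocol deviations that would impact the evaluation of efficacy" and (iii) "have at least 80% overall treatment compliance". Protocol 10.2 has the same threshold: "have at least 80% overall dosing compliance". Criterion (iii) is the only numeric adherence test in either definition. PP exclusions are settled before database lock and unmasking.

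Three other provisions bear on the point:

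- SAP 10.1.3 makes the PP analysis the first sensitivity analysis for both primary endpoints.
- SAP 6.4.3.1 states: "For subjects who prematurely discontinue the study without taking rescue medication, the LOCF approach will be used to impute the missing data". The value carried is the last one obtained up to two days after the last dose.
- Protocol 8.5.2 states: "Under-dosing will not be reported as a protocol deviation until the subject has missed both of the doses on 2 or more consecutive days". Whether that deviation is major or minor depends on the size of the shortfall, with no cut-off given.

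**The concern.** A PP analysis is meant to show whether the result holds in subjects treated broadly as planned. Here the adherence test measures only how regularly a subject dosed while still dosing. Skipping doses lowers the score, but abandoning the course does not. A subject can take about a fifth of the planned doses and still show perfect compliance.

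Such a subject may also have little outcome data. If the subject leaves the study without rescue, the POD8 and POD15 values used for the primary endpoints are carried forward from an early visit. The PP analysis could then include responders whose status rests on a short exposure and a single observation, which weakens it as support for the ITT result.

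**Working it through.** **Inputs**

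- Regimen: 2 doses a day for 14 days (SAP 3.1).
- Cut-off: 80% (SAP 5.2, protocol 10.2).
- Duration: first dose date to the subject's last dose date (SAP 9); the day-count convention is not stated there.
- 370 subjects, 5% dropout (SAP 4).

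**Step 1: the plan's own figure.** 14 × 2 = 28 doses, which agrees with SAP 11.1. The documents give no worked compliance value.

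**Step 2: the bracket.** Read left to right as printed, the factor 2 multiplies. A perfect full course gives 28/14 × 2 × 100 = 400%, and 6 doses in 3 days gives 6/3 × 2 × 100 = 400%. The intended form must be doses/(days × 2), which is used below. This printing fault is separate from the present point, and correcting it does not remove the problem.

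**Step 3: the day count.** A plain date difference gives a perfect full-course subject 28/(13 × 2) = 107.7%, and gives a subject dosed on one day only a zero denominator. SAP 11.1 describes duration in the same terms and uses categories from 1 day up to 14 or more. Both facts point to an inclusive count (last − first + 1).

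**Step 4: compliance by type of subject.**

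| Subject | Doses | Inclusive days | Plain date difference | Share of 28 planned |
|---|---|---|---|---|
| Full course | 28 | 28/(14 × 2) = 100% | 28/(13 × 2) = 107.7% | 100% |
| Stops after day 3, none missed | 6 | 6/(3 × 2) = 100% | 6/(2 × 2) = 150% | 21.4% |
| Stops after day 5, none missed | 10 | 10/(5 × 2) = 100% | 10/(4 × 2) = 125% | 35.7% |
| Doses to day 14, misses 6 | 22 | 22/(14 × 2) = 78.6% | 22/(13 × 2) = 84.6% | 78.6% |

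In general, a subject who stops after day d with no missed dose scores 2d/(2d) = 100% for every d from 1 to 14. The early-stopper result therefore does not depend on the day-count convention: such a subject passes criterion (iii) either way.

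**Step 5: how one early value can reach POD15.** Suppose the last dose is on day 3, pain is grade 0 at the POD4 visit, and the subject then withdraws without rescue. POD4 is within two days of the last dose, so SAP 6.3.5 and 6.4.3.1 allow that value to be used and carried to POD8 and POD15. The subject is then a pain responder on one observation. SAP 10.1.2 provides a category for responders with imputed data.

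**Step 6: scale.** 370 × 0.05 = 18.5, so about 18 subjects if every assumed dropout were affected.

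**The case against.** **Passing the 80% test is not PP membership.** A reader might infer that the 3-day stopper stays in the PP set. The documents do not establish that. Criterion (ii) applies separately, and protocol 8.5.2 grades under-dosing against the protocol course, so 11 undosed days could be a major deviation. Protocol Appendix A expressly records pandemic-related early terminations as deviations. This objection stands, and it limits the point to what criterion (iii) does. It does not assure exclusion, however. Protocol 8.5.2 has no cut-off and does not say whether doses after withdrawal count as missed. Protocol 6.3 lets a subject stop freely and then withdraws that subject.

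**The subject with 22 of 28 doses is not evidence against the denominator.** A reader might infer that the formula perversely removes this better-treated subject. Removal requires the inclusive count (84.6% passes on a plain difference), and 22/28 = 78.6% also fails against planned doses. That is the ordinary effect of an 80% cut-off.

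**Other analyses cover part of the gap.** In SAP 10.1.3 the Completed-Case analysis leaves out a subject withdrawn early, and the Observed-Case analysis counts subjects with missing assessments as non-responders, which removes the benefit of LOCF. SAP 7.1 and 11.1 tabulate early discontinuation of study drug, duration and dose counts. It would therefore be too strong to say that the plan has no check on early stoppers. What remains is that neither of those two analyses selects subjects by doses taken.

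**The figure of 18 is not an estimate.** It includes dropouts after POD15 who finished dosing, subjects who would be excluded anyway, and Investigator stops that the proposed rule would not change.

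**Compliance while on treatment is a coherent measure, and LOCF applies equally in the ITT analysis.** Both statements are true. They support keeping the SAP 9 figure as a description, but not as the PP adherence test.

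**Conclusion.** The point holds in this form: criterion (iii) cannot detect early stopping, and exclusion of early stoppers is left to case-by-case deviation grading without a stated threshold. The clearest example is 100% compliance for 6 of 28 planned doses (21.4%). This assumes that the bracket is corrected to doses/(days × 2) and that days are counted inclusively; a plain date difference gives 150% and the same decision.

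The number of subjects whose PP status would change is unknown. It is below about 18 of 370 if the 5% dropout assumption holds. Carry-forward into the PP analysis arises only for those who are kept under criterion (ii), were not rescued and left before POD15. The primary analysis is on the ITT population and is unaffected. This is a cheap improvement to a supportive analysis and no threat to the trial's main conclusion.

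**What to change.** Amend SAP 9 and 5.2 before database lock, when PP exclusions are settled:

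- For PP criterion (iii), define compliance as doses instilled correctly divided by the 28 planned doses.
- For subjects who are rescued, or whose study drug is stopped by the Investigator, use the doses due up to that stop. State this as a pre-specified rule. It will keep some short-course subjects, but as an explicit choice.
- Keep the actual-duration figure as a descriptive exposure summary only, with the bracket corrected and the inclusive day count written out.

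A lesser alternative keeps the present denominator and states whether a voluntary early stop is a major deviation for PP purposes. That closes the gap in criterion (ii) but leaves the 80% figure uninformative about the course.

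The cost is SAP wording and one derivation. The downside is a slightly smaller PP set. No data collection changes, because doses and dates are already recorded in the diary and eCRF.
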